## **Background and Introduction**

Parkinson's disease (PD) is characterized by the gradual onset of motor symptoms such as bradykinesia, rigidity, tremor, gait difficulties and postural instability, as well as non-motor symptoms such as cognitive impairment and autonomic dysfunction among others [1]. Neurogenic orthostatic hypotension (nOH) is the main clinical manifestation of cardiovascular autonomic dysfunction [2]. The arterial baroreflex allows for beat-to- beat regulation of the blood pressure and heart rate via differential modulation of its cardiovagal (parasympathetic) and noradrenergic (sympathetic) efferent limbs [3]. Several mechanisms may contribute to nOH in PD including baroreflex-cardiovagal and baroreflex-sympathetic noradrenergic failure [2]. The prevalence of nOH in PD increases with age and disease duration; however, several studies have documented that nOH may appear early in the course of PD and reported prevalence of nOH in PD ranges from 30% to 65% [4, 5]. The presence of nOH in PD is associated with poor outcomes related to cardiovascular events, increased morbidity and mortality, more rapid disease progression, cognitive impairment, and falls [6].

Levodopa is a precursor of dopamine and is the treatment of choice to treat the motor symptoms of PD; however, the effect of levodopa on cardiovascular autonomic function in PD is poorly understood. Orthostatic hypotension has been documented as a potential side effect of levodopa in different studies [7, 8]. As a result, clinicians may be reluctant to prescribe levodopa in patients with PD with nOH (PD+OH), which leads to suboptimal management of motor symptoms. On the other hand, several studies failed to show any clear relationship between levodopa and orthostatic hypotension in patients with PD [9-12]. Important limitations of prior studies include the lack of detailed investigation of baroreflex cardiovagal and sympathetic noradrenergic functions and the fact that the same patients were not tested on and off levodopa.

We propose to investigate the effects of levodopa on cardiovascular autonomic function in patients with PD+OH and PD without nOH (PD-OH) by performing standardized autonomic testing in the same patients on and off levodopa.

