## Sample Size:

At Utah:

All Centers: 40

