#### For PD+OH group:

- Orthostatic hypotension defined by sustained drop in systolic blood pressure > 20 mmHg and/or a drop in diastolic blood pressure > 10 mmHg within 3 minutes from supine to standing during active standing or tilt [14].
- Autonomic testing and a ratio orthostatic heart rate change / systolic blood pressure change < 0.5 bpm/mmHg will confirm a neurogenic etiology [15].

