#### **Procedures:**

**Screening:** When the PI (or approved study personnel) makes contact with potential participant, basic information will be obtained to determine eligibility, including: medical history, PD diagnosis date and symptoms, current medications, among others.

Consent Process: Informed consent will be completed. Participants will complete the informed consent form on paper, or via REDCap. Participants will receive a paper copy per their request. Prior to signing the consent form, study personnel will thoroughly explain all study procedures and provide participants with ample time to ask any questions. The study team will continue to provide participants with opportunities to ask questions to ensure ongoing informed consent throughout the progress of the study.

Clinical assessment: The primary investigator will perform a medical history and physical examination before the testing procedures (baseline visit). The baseline visit will be performed on levodopa. The scales and assessments will include the Composite Autonomic Symptoms Score 31 (COMPASS 31), the Movement Disorder Society-Sponsored Revision of the Unified Parkinson's Disease Rating Scale (MDS-UPDRS) part I, II, III, and Hoehn and Yahr stage. The clinical assessment and scales are part of the standard of care in PD. Orthostatic vital signs (standing and supine measures of heart rate and blood pressure) will be performed during the baseline visit with active standing and the day of off-levodopa autonomic testing.

**Autonomic testing:** All participants will undergo autonomic testing on two separate days. The first autonomic testing will occur within 4 weeks of the baseline visit. The two autonomic tests will occur within a 2-week timeframe. To avoid any confounding of treatment effects and period effects, the order of testing (on versus off levodopa) will be randomized so testing on the first day will be on-levodopa for half of the participants and off-levodopa for the other participants. The procedures performed in this study are part of standardized clinical autonomic function testing. Autonomic testing will be performed by a research assistant with expertise in autonomic testing.

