# Statistical Methods, Data Analysis and Interpretation

Summary statistics will be used to describe demographic and clinical variables. A sample size of 40 will achieve a power of 80% and a level of significance of 5%, for detecting a mean of 8 mmHg in ΔSBP-3' between the ON and OFF states with a within subject standard deviation of 20 mmHg based on published data on the effect of levodopa on supine and standing blood pressure in people with PD. The main statistical analysis will be conducted using mixed-effects regression models (linear mixed models), which will allow for the correlation of repeated measures within subjects. The response variable in our models will be ΔSBP-3', and the primary predictors will be the ON vs. OFF levodopa state and the period (visit 2 versus visit 3). A random intercept will be included for each subject to account for the within-subject correlation. For analyses of secondary outcomes, we will fit a mixed effect model and adjust the p value for multiple comparisons using the Hochberg multiple comparison procedure. Changes in blood pressure and heart rate with active standing and indices of baroreflex cardiovagal and sympathetic noradrenergic function OFF levodopa will be compared between PD+OH and PD-OH with Student t tests.

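### The PD+OH versus PD-OH comparisons name Student t tests although neither equal group sizes nor equal spread is secured; Welch's test is the safer choice at a small cost

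*Combined protocol and SAP*

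**What the plan says.** The Combined protocol and SAP describes the between-group comparison in the last sentence of Statistical Methods, Data Analysis and Interpretation. The outcomes are "Changes in blood pressure and heart rate with active standing and indices of baroreflex cardiovagal and sympathetic noradrenergic function OFF levodopa", and they "will be compared between PD+OH and PD-OH with Student t tests". The section mentions no unequal-variance version, variance check, transformation or rank-based alternative, and it gives no standard deviation by group for any outcome.

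Group sizes are not set. Sample Size gives only "All Centers: 40". The one half-and-half allocation, under Procedures, concerns test order: "testing on the first day will be on-levodopa for half of the participants". It does not concern orthostatic hypotension status.

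The inclusion criteria for the PD+OH group begin with "Orthostatic hypotension defined by sustained drop in systolic blood pressure > 20 mmHg and/or a drop in diastolic blood pressure > 10 mmHg", so membership depends on the blood-pressure response. Background and Introduction says that "reported prevalence of nOH in PD ranges from 30% to 65"%.

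**The concern.** Student's t test combines the two group variances into one estimate, weighted by degrees of freedom. When the groups differ in size and in true spread, that estimate gives the wrong standard error for the difference in means. If the smaller group is the more variable, the standard error is too small and false positives rise. If the larger group is the more variable, it is too large and the test becomes too strict.

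Both conditions could arise here. Nothing in the plan forces equal groups. One group is also chosen for an abnormal haemodynamic response, so equal spread cannot be taken for granted. What is at stake is whether p values for PD+OH versus PD-OH differences in the baroreflex indices mean what they appear to mean.

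**Working it through.** **The plan's own figure.** The only stated design figure is the 40: "A sample size of 40 will achieve a power of 80% and a level of significance of 5"%. It belongs to another contrast, the primary ON/OFF comparison, where the target difference is 8 mmHg and the SD 20 mmHg. Reading 20 as the SD of the ON-OFF difference and the 5% as one-sided, n = (20 × (1.645 + 0.842) / 8)² = 38.6, so 39 by the normal formula (41 by the t distribution). A two-sided 5% gives (20 × (1.960 + 0.842) / 8)² = 49.1, so 50. The plan states neither reading. The figure says nothing about the between-group tests, for which no level, power or size is given.

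**Inputs for the check.**
- Total 40 (Sample Size).
- PD+OH share 30% to 65% (Background and Introduction): 0.30 × 40 = 12 and 0.65 × 40 = 26, so splits of 12:28 to 26:14. It is an assumption that enrolment follows prevalence.
- SD ratio, PD+OH over PD-OH, 0.5 to 3. This is an assumption, since the documents give no group SDs.
- Normal data, true difference zero, nominal two-sided 5%.

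**Formulas.** Student: t = (m₁ − m₂) / √[s_p²(1/n₁ + 1/n₂)], with s_p² = [(n₁ − 1)s₁² + (n₂ − 1)s₂²] / (n₁ + n₂ − 2). Welch: t = (m₁ − m₂) / √(s₁²/n₁ + s₂²/n₂), with df = (s₁²/n₁ + s₂²/n₂)² / [(s₁²/n₁)²/(n₁ − 1) + (s₂²/n₂)²/(n₂ − 1)].

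**Direction by hand**, with PD+OH SD 2 and PD-OH SD 1:
- 12:28. True variance of the difference: 4/12 + 1/28 = 0.369. Pooled version: [(11 × 4 + 27 × 1)/38] × (1/12 + 1/28) = 1.868 × 0.1190 = 0.222. The standard error is √(0.222/0.369) = 0.78 of its true size, about 22% too small.
- 26:14. True: 4/26 + 1/14 = 0.225. Pooled: [(25 × 4 + 13 × 1)/38] × (1/26 + 1/14) = 2.974 × 0.1099 = 0.327. The standard error is √(0.327/0.225) = 1.20 of its true size, about 20% too large.
- 20:20. True: 4/20 + 1/20 = 0.25. Pooled: 2.5 × 0.1 = 0.25. The two agree.

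**Simulated error of Student's test** (400,000 data sets per cell):

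| PD+OH:PD-OH | ratio 0.5 | 1 | 1.5 | 2 | 3 |
|---|---|---|---|---|---|
| 12:28 | 1.4% | 5.0% | 9.4% | 12.9% | 16.9% |
| 16:24 | 2.9% | 5.0% | 7.0% | 8.5% | 10.2% |
| 20:20 | 5.2% | 5.0% | 5.1% | 5.3% | 5.5% |
| 26:14 | 10.6% | 5.0% | 2.9% | 2.1% | 1.5% |

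Welch's test stays between 4.9% and 5.2% in all of these cells. In more extreme splits, from 8:32 to 30:10, it stays between 4.9% and 5.3%.

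**Cost of Welch when variances are equal**, true difference 0.9 SD: power goes from 79.1% to 79.0% at 20:20, from 72.0% to 69.9% at 12:28, and from about 67.1% to 63.6% at 10:30. The last split is 25% PD+OH, just outside the protocol's prevalence range.

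**The case against.** Several points on the other side are sound.

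- **The level.** A reader might infer that the trial's stated 5% level is compromised. The documents do not support that. The 5% is attached to the sample size for the primary ON/OFF contrast, which is analysed by a mixed model. For the between-group t tests, 5% is only the conventional nominal level.
- **The direction.** A reader might infer that PD+OH is the more variable group and that false positives are therefore inflated. No group SDs are given, and the outcomes are varied. The neurogenic criterion limits heart-rate change relative to the systolic drop, so a narrower heart-rate spread in PD+OH is possible. At a ratio of 0.5 the pattern reverses.
- **Both conditions are needed.** With equal groups the error is within about half a point of 5%, and with equal spread it is right at any split. The group-specific inclusion criteria and the chart review for eligibility would allow recruitment by group, and no section says that enrolment will follow prevalence.
- **The null hypothesis.** The groups differ by construction on active-standing blood pressure, so a false-positive rate has little meaning there. It matters chiefly for the baroreflex indices, and even among those some true differences are likely.
- **The role of the tests.** Objectives names the baroreflex indices as the Aim 2 endpoint, so a reader might infer that Aim 2 rests on these tests. A comparison made OFF levodopa does not test whether levodopa's effect differs between the groups.
- **The cost.** Welch's test is not free when groups are unequal and variances equal.

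These points limit the size and reach of the concern. None gives a reason to pool the variances when the group split and the spreads are both unknown at the planning stage.

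**Conclusion.** The concern holds as a minor, easily mended point. Within splits of 12:28 to 26:14 and SD ratios of 0.5 to 3, a nominal 5% Student test has a true error between about 1.4% and 17%, and the plan gives no means of knowing beforehand which side of 5% it will fall on. The result rests on three things: Student being read in its usual pooled sense, enrolment tracking the quoted prevalence, and SD ratios that are assumed. The simulation also takes the data as normal. Pressure recovery time and the Valsalva areas cannot fall below zero and may be skewed. Welch's test deals with unequal spread, not with skewness.

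**What to change.** In Statistical Methods, Data Analysis and Interpretation, replace Student t tests with Welch (unequal-variance) t tests for the PD+OH versus PD-OH comparisons, to be used without a preliminary variance test. It would help, though it is optional, to state that they are two-sided at a nominal 5% and to give intended group sizes, since near-equal groups remove most of the difficulty.

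The change is a few words. It touches no procedure and no other analysis. Its price is the power loss shown in the working: negligible near balance, and about 2 to 3.5 points in clearly unequal groups if the variances turn out to be equal.
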